1.0 PURPOSE

The purpose of this statistical analysis plan (SAP) is to outline the primary statistical analyses for the Fixation using Alternative Implants for the Treatment of Hip Fractures (FAITH-2): A Multi-Centre 2x2 Factorial Randomized Trial Comparing Sliding Hip Screws versus Cancellous Screws AND Vitamin D versus Placebo on Patient Important Complications and Quality of Life in the Treatment of Young Adult (18-60) Femoral Neck Fractures manuscript. This SAP includes review of all data collected. The FAITH-2 Writing Committee will determine which data points will be included in the primary manuscript and supplemental documents. We will adhere to the CONSORT 2010 guideline when reporting the results of FAITH-2. Additional SAPs will be developed for secondary analyses.

2.0 STUDY SUMMARY

Title	Fixation using Alternative Implants for the Treatment of Hip Fractures (FAITH-2): A Multi-Centre 2x2 Factorial Randomized Trial Comparing Sliding Hip Screws versus Cancellous Screws AND Vitamin D versus Placebo on Patient Important Outcomes and Quality of Life in the Treatment of Young Adult (18-60) Femoral Neck Fractures
Short Title	FAITH-2
Methodology	Concealed 2x2 factorial randomized controlled trial
Clinical Sites	Multiple international clinical sites
Primary Objective	The primary objective is to assess the impact of surgical implant (sliding hip screws (SHS) versus cancellous screw (CS) fixation) AND nutritional supplementation (vitamin D versus placebo) on a composite of patient important outcomes during the 12 month post-surgery follow-up period. The composite of patient important outcomes includes: re-operation, femoral head osteonecrosis, severe femoral neck malunion, and nonunion.
Secondary Objectives	To assess the impact of surgical implant (sliding hip screw fixation versus cancellous screw fixation) and nutritional supplementation (vitamin D versus placebo) on health-related quality of life and functional outcomes, fracture healing complications, and radiographic fracture healing.
Sample Size	We will recruit a sample size of 808 patients with full follow-up. Based on an anticipated 10% loss to follow-up, 898 patients will need to be enrolled in the FAITH-2 trial.
Diagnosis and Main Inclusion Criteria	Femoral neck fracture in patients between the ages of 18 and 60.
Study Products	Surgical implants: Sliding hip screw versus multiple cancellous screws. Nutritional supplementation: Vitamin D ₃ (4,000 International Units/day taken for 6 months) versus placebo taken for 6 months.
Length of Follow-Up	12 months.

3.0 SCREENING AND ENROLMENT

The number of participants screened, included, and excluded will be presented in separate flow diagrams by surgical treatment and nutritional supplementation groups (**Figures 1 and 2**). The figure will include the number of patients who were eligible, ineligible, and randomly assigned to the two treatment groups. It will also include the number of participants who are lost to follow-up over the course of the study. The number of patients excluded by reason will be summarized in **Table 1**.

Figure 1: Flow Diagram – Surgical Treatment

[figure not shown]

Figure 2: Flow Diagram – Nutritional Supplementation

[figure not shown]

Table 1: Reasons for Exclusion at Screening

Reasons for Exclusion	Number of Patients N=	Number of Patients Excluded Due to Randomization Errors				Total N=
		Surgical Treatment X N=	Surgical Treatment Y N=	Nutritional Supplementation X N=	Nutritional Supplementation Y N=	
Inclusion Criteria						
The patient is not between the ages of 18 and 60 years						
The patient does not have a femoral neck fracture						
The fracture is not amenable to both surgical treatments (SHS and cancellous screw)						
Operative treatment will not take place within 7 days of injury						
Exclusion Criteria						
The patient has previously been diagnosed with osteoporosis						
The patient has a fracture-dislocation of the femoral neck and hip joint						
The patient has planned antegrade nailing of an ipsilateral femoral shaft fracture (if present)						
The patient has an infection around the hip (i.e. soft tissue or bone)						
The patient has a stress fracture of the femoral neck						
This is a pathological fracture secondary to neoplasm or other bone lesion						
The patient has a known or likely undiagnosed disorder of bone metabolism such as Paget's disease, osteomalacia, osteopetrosis, osteogenesis imperfect, etc						
The patient is currently taking an over counter drug and/or food supplement that contains vitamin D and is unable or unwilling to discontinue its use for this study						
There are likely problems, in the judgement of the attending surgeon, with						

maintaining follow-up (e.g. patients with no fixed address, plans to move out of town). This may include patients with severe mental disorders and drug addictions without adequate support						
The patient is pregnant						
The patient is incarcerated						
The patient is not expected to survive their injuries						
The patient or substitute decision maker has not provided informed consent						
The patient is eligible, but was not randomized due to error						

4.0 PARTICIPANT DEMOGRAPHICS CHARACTERISTICS

Participant demographic, baseline characteristics, and major comorbidities of the population will be summarized by surgical treatment and nutritional supplementation groups (**Table 2**). Descriptive statistics will be used to summarize the demographic data. Means and standard deviations (SDs) will be used for continuous data, and categorical data will be presented as frequencies and proportions.

Table 2: Participant Demographics

Characteristic	Variable	Surgical Treatment X N=43	Surgical Treatment Y N=43	Nutritional Supplementation X N=	Nutritional Supplementation Y N=	Total N=86
Age, mean (SD) (years)	2.1 Q5, 3.1 Q1					
Sex, n (%) Male Female	3.1 Q2					
Ethnicity, n (%) Native/Aboriginal South Asian East Asian Southeast Asian (Filipino) Hispanic/Latino White/Caucasian Black (African/Caribbean) Mixed (Black & White) Middle Eastern	3.1 Q3					

Characteristic	Variable	Surgical Treatment X N=43	Surgical Treatment Y N=43	Nutritional Supplementation X N=	Nutritional Supplementation Y N=	Total N=86
Body Mass Index (BMI) (kg/m ²), n (%) Underweight <18.5 Normal weight 18.5-24.9 Overweight 25-29.9 Obese 30-39.9 Morbidly Obese ≥40	3.1 Q4, Q5					
Work-Related Injury, n (%)	3.1 Q7					
History of Smoking, n (%) Yes Previously smoked but quit No	3.1 Q8					
Consumption of Alcohol, n (%)	3.1 Q9					
Current Medications, n (%) None Nonsteroidal Anti-Inflammatory Drugs Steroid Medications Calcium Vitamin D	3.2 Q11					
Major Comorbidities, n (%) None One Two Three Four Five	3.2 Q12					

5.0 INJURY AND FRACTURE CHARACTERISTICS

Injury details and fracture characteristics will be summarized in **Table 3**. Pre-operative and post-operative care details (**Table 4**) will be presented for each surgical treatment and nutritional supplementation group. Means and SDs will be used for continuous data, and categorical data will be presented as frequencies and proportions.

Table 3: Fracture Characteristics

Characteristic	Variable	Surgical Treatment X N=	Surgical Treatment Y N=	Nutritional Supplementation X N=	Nutritional Supplementation Y N=	Total N=
Level of the Fracture Line, n (%) Subcapital Midcervical Basal Unable to assess	Adjudicated Data					
Garden Classification, n (%) Garden I (undisplaced) Garden II (undisplaced) Garden III (displaced) Garden IV (displaced) Unable to assess	Adjudicated Data					
Pauwels' Classification, n (%) Type I Type II Type III Unable to assess	Adjudicated Data					
Mechanism of Injury, n (%) Motor Vehicle Accident (Driver/Passenger) Motor Vehicle Accident (Pedestrian) Motorcycle Accident Recreational Vehicle (4 Wheeler, Snowmobile, ATV, etc) Bicycle Accident Fall from Height (>1m) Fall from Height (≤1m) Fall from Standing Direct Trauma (Blunt) Direct Trauma (Penetrating)	3.3 Q15					
Additional Fractures, n (%) Upper extremity Lower extremity Spine and sacrum Pelvis	3.4 Q20					
Additional Injuries, n (%) Chest Injury Abdominal Injury Head/Neck Injury Soft Tissue Injuries to Extremities	3.4 Q24					

Characteristic	Variable	Surgical Treatment X N=	Surgical Treatment Y N=	Nutritional Supplementation X N=	Nutritional Supplementation Y N=	Total N=
Ipsilateral Femoral Shaft Fracture, n (%)	3.5 Q23					

Table 4: Summary of Pre-Operative and Post-Operative Care Details

Characteristic	Variable	Surgical Treatment X N=	Surgical Treatment Y N=	Nutritional Supplementation X N=	Nutritional Supplementation Y N=	Total N=
Pre-operative Antibiotic Prophylaxis, n (%)	3.5 Q26					
Discharge Location, n (%) Home Rehabilitation Facility Other Hospital Medical Respite	7.1 Q2					
Provided with Nutritional Supplement, n (%)	7.1 Q3					
Received Nutritional Supplement Within Two Weeks of Femoral Neck Surgery, n (%)	7.1 Q5					
Nutritional Instructions and Importance of Complying with Nutritional Supplementation Discussed with Participant, n (%)	7.1 Q6					

6.0 SUMMARY OF SURGICAL PROCEDURES

The following sections will summarize the surgical procedures. General surgical characteristics and the surgical details for each surgical treatment and nutritional supplementation group will be presented. Means with SDs will be used for continuous data, and categorical data will be presented as frequencies and proportions (Tables 5, 6, and 7).

Table 5: General Surgical Characteristics

Surgery Characteristic	Variable	Surgical Treatment X N=	Surgical Treatment Y N=	Nutritional Supplementation X N=	Nutritional Supplementation Y N=	Total N=
Time from Injury to Surgery, mean (SD) (hours)	3.3 Q13, 4.1 Q1/Q2					
Length of Procedure, mean (SD) (minutes)	4.1 Q2/Q3					
Attending Surgeon Present in Operating Room for Critical Aspects of Procedure, n (%)	4.1 Q5					

Surgery Characteristic	Variable	Surgical Treatment X N=	Surgical Treatment Y N=	Nutritional Supplementation X N=	Nutritional Supplementation Y N=	Total N=
Who Performed Majority of Procedure, n (%) Surgeon Fellow Resident	4.1 Q6					
Total Blood Loss, mean (SD) (mL)	4.1 Q7					
Type of Reduction Used, n (%) Closed Open None	4.1 Q8					
Procedure Performed, n (%) CS SHS Cephalomedullary Nail	4.1 Q9					
Implant Manufacturer, n (%) Synthes Biomet Stryker Smith & Nephew DePuy Hansson Zimmer	4.1 Q10					
Capsulotomy Performed, n (%)	4.2 Q11					
Aspiration of Intracapsular Hematoma, n (%)	4.2 Q12					
Additional Buttress-type Plates Used, n (%)	4.2 Q13					
Injectable Bone Substitutes Used, n (%)	4.2 Q14					
Bone Graft Used, n (%)	4.2 Q15					
Other Procedures Performed During Same Operation as Femoral Neck Fracture Internal Fixation, n (%)	4.2 Q16					
Treatment of Ipsilateral Femoral Neck Fracture, n (%) N/A (No Ipsilateral Shaft Fracture) Plating Retrograde Nailing Antegrade Nailing	4.2 Q18					
Re-operations Planned For Patient's Fractured Hip, n (%) Irrigation and Debridement Wound Closure Implant Revision Implant Exchange Implant Adjustment	4.3 Q19					

Surgery Characteristic	Variable	Surgical Treatment X N=	Surgical Treatment Y N=	Nutritional Supplementation X N=	Nutritional Supplementation Y N=	Total N=
Bone Graft Femoral Shaft Fracture Surgery						

Table 6: CS Surgical Management

*to be completed only after unblinding

CS Characteristic	Variable	CS N=
Number of Screws Used, n (%) Three Four	5.1 Q2	
Diameter of Screws, mean (SD) (mm)	5.1 Q3	
Number of Partially Threaded Screws with Short Threads Used, n (%) Zero One Two Three Four	5.1 Q4	
Number of Partially Threaded Screws with Long Threads Used, n (%) Zero One Two Three Four	5.1 Q5	
Formation of Screws (or Pins), n (%) Triangle (Apex at Top) (3 Screws) Inverted Triangle (Apex at Bottom) (3 Screws) Square (4 Screws) Diamond (4 Screws) Other	5.1 Q6	
Aiming of Screws (or Pins), n (%) Parallel Crossed	5.1 Q7	
Number of Washers Used, n (%) Zero One Two Three Four	5.1 Q8	
Use of Hook Pins or Any Other Non-Screw Implants, n (%)	5.1 Q9	

Table 7: SHS Surgical Management

*to be completed only after unblinding

SHS Characteristic	Variable	SHS N=
Type of Sliding Fixed-Angle Plate Construct Used, n (%) Traditional Large Diameter Hip Screw Spiral/Helical Blade Dynamic Hip Screw	6.1 Q2	
Implant Position in Head of Femur, n (%) Centre-Centre Position Superior Position Anterior Position Inferior Position Posterior Position Other (specify):	6.1 Q3	
Number of Holes in Side Plate, n (%) Two Three Four	6.1 Q4	
Number of Cortical Screws in Side Plate, n (%) Two Three Four	6.1 Q5	
Supplemental (Derotational) Screws Included in Fixation, n (%) With Washer Without Washer	6.1 Q6	
Used of Compression Screw, n (%)	6.1 Q7	
Final Tip Apex Distance, mean (SD) (mm)	6.1 Q8	

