4.5.4 Adherence to Surgical Intervention

Crossovers rates between the SHS and multiple cancellous screw groups are likely to be low because both implants are inserted with similar techniques and surgeon expertise in both techniques is likely to be very similar. Participants will be randomized as close to surgery as possible. Any participants who crossover will be analyzed in the group to which they were allocated, maintaining the intention to treat approach for the analysis.

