4.11 Blinding

Surgeons, research personnel, participants, and members of the CAC cannot be blinded to the treatment allocation of the surgical interventions (SHS versus cancellous screws).

The data analyst and the Steering Committee will be blinded to the surgical treatment allocation.

The complete blinding of the nutritional supplement will be achieved by using vitamin D₃ and placebo liquid products that are indistinguishable. This will ensure that the surgeon, participants, research personnel, the CAC members, the data analyst, and the Steering Committee are blinded to the participants' nutritional supplementation allocation. An unblinding procedure will be made available when necessary (**Figure 6**).

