8.0 PRIMARY CLINICAL ENDPOINT

The primary analyses will first be completed using only blinded treatment groups. All outcome analyses will be performed using the intention to treat approach. The FAITH-2 study primary clinical endpoint is a composite of patient important outcomes that occur within the 12 months post-surgery follow-up period (**Table 9**). Specifically, these are limited to 1) re-operation, 2) femoral head osteonecrosis, 3) severe femoral neck malunion, and 4) nonunion.

The first analysis of clinical outcomes will be a Cox regression with main effects for implant type and supplementation, and the interaction between the two. If the interaction is not significant at $\alpha=0.05$ we will perform two independent comparisons between the treatment groups (SHS versus cancellous screws AND separately vitamin D₃ supplementation versus placebo) using the chi-square statistic and an alpha level of 0.05 for the composite of patient important outcomes (**Tables 10 and 11**).

If the interaction is significant we will keep this interaction term in all subsequent analyses, and present two hazard ratios (HRs) with 95% confidence intervals (CIs) for the surgical intervention and two HRs for the nutritional supplementation (i.e. We will report an HR for SHS versus cancellous screws in those who receive vitamin D, and a separate HR for SHS versus cancellous screws in those who receive placebo. We will also report an HR for vitamin D versus placebo in those who receive SHS, and a separate HR for vitamin D versus placebo in those who receive cancellous screws) The results will be summarized in **Table 12**. Kaplan-Meier curves will also be constructed.

Table 9: Primary Clinical Endpoint Components and Reasons for Secondary Procedures

Outcome	Definition
Unplanned Secondary Procedures (study event)	
Any unplanned surgery related to the treatment of the femoral neck fracture. Specific unplanned secondary procedures include:
 
 • Implant removal • Bone graft • Wound closure • Proximal femur osteotomy • Implant exchange – THA • Implant exchange – HA • Implant exchange – CS • Implant exchange – SHS • Implant exchange – Other IF • Soft tissue procedure • Dynamization • Osteochondroplasty

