Re-operation	Adjudicated Data				
Procedure for Nonunion Implant removal Bone graft Proximal femur osteotomy Implant exchange – THA Implant exchange – IF	Adjudicated Data				
Procedure for Femoral Head Osteonecrosis Implant removal Implant exchange – THA	Adjudicated Data				
Procedure for Deep Infection Wound closure Implant exchange – SHS Soft tissue procedure	Adjudicated Data				
Procedure for Painful Hardware Implant removal Bone graft Implant exchange – THA	Adjudicated Data				
Procedure for Screw Penetration Implant removal	Adjudicated Data				
Procedure for Post-Traumatic Arthritis Osteochondroplasty	Adjudicated Data				
Procedure for IT Fracture Implant exchange – IF	Adjudicated Data				
Procedure for Relieving Pain Implant exchange – THA	Adjudicated Data				
Femoral head osteonecrosis					
Femoral head osteonecrosis	Adjudicated Data				
Severe femoral neck malunion					
Severe femoral neck malunion	Adjudicated Data				
Nonunion					
Nonunion	Adjudicated Data				

Table 12: Primary Clinical Endpoint (Significant Interaction Between Implant Type and Supplementation Present)

End Point	Variable	Overall N=	Surgical Treatment X N=	Surgical Treatment Y N=	Nutritional Supplementation X N=	Nutritional Supplementation Y N=	Hazard Ratio (95% CI)				P- Value
							Surgery X + Supplement X vs. Surgery Y + Supplement X	Surgery X + Supplement Y vs. Surgery Y + Supplement Y	Surgery X + Supplement X vs. Surgery X + Supplement Y	Surgery Y + Supplement X vs. Surgery Y + Supplement Y	
Primary Clinical Endpoint: re-operation, femoral head osteonecrosis, severe femoral neck malunion, nonunion	Adjudicated Data										
Primary Clinical Endpoint Components											
Malunion Implant removal Bone graft Wound closure Proximal femur osteotomy Implant exchange – THA Implant exchange – HA Implant exchange – IF (crossover) Implant exchange – IF (original) Implant exchange – Intramedullary nailing Implant exchange – curved plate and IF Implant exchange – 110 degree blade plate Soft tissue procedure Dynamization Osteochondroplasty	Adjudicated Data										
Nonunion Implant removal	Adjudicated Data										

Bone graft Wound closure Proximal femur osteotomy Implant exchange – THA Implant exchange – HA Implant exchange – IF (crossover) Implant exchange – IF (original) Implant exchange – Intramedullary nailing Implant exchange – curved plate and IF Implant exchange – 110 degree blade plate Soft tissue procedure Dynamization Osteochondroplasty											

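### Nothing in the SAP stops Table 5 from revealing, before unblinding, which masked surgical code is which implant

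*Combined protocol and SAP*

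**What the plan says.** Protocol 4.11 states that surgeons, research personnel, participants and adjudicators cannot be blinded to the implant. For the surgical comparison it then promises: "The data analyst and the Steering Committee will be blinded to the surgical treatment allocation". SAP 8.0 sets the order of work: "The primary analyses will first be completed using only blinded treatment groups".

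SAP 6.0 introduces Tables 5 to 7: "General surgical characteristics and the surgical details for each surgical treatment and nutritional supplementation group will be presented". Table 5 is laid out under the masked headings Surgical Treatment X and Y. One of its rows, taken from case report form item 4.1 Q9, is "Procedure Performed, n (%) CS SHS Cephalomedullary Nail". The next row, from item 4.1 Q10, gives the implant manufacturer.

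Tables 6 and 7 describe the screw and sliding hip screw operations. Each carries the note "to be completed only after unblinding". Table 5 carries no such note, and no other section defers it, limits who sees it, or gives it to a separate unblinded analyst.

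On crossover, protocol 4.5.4 says: "Crossovers rates between the SHS and multiple cancellous screw groups are likely to be low". It gives no figure.

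**The concern.** A masked column that reports the name of the implant used is masked only if many patients received the implant to which they were not allocated. The protocol expects the opposite, so anyone who reads the Procedure Performed row by X and Y learns the code.

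This matters because the implant is open to almost everyone else. Masking at the analysis stage is the only masking left for the surgical comparison. It protects decisions that the SAP leaves open: missing data are covered by one sentence naming multiple imputation without a model (SAP 10.0), and the longitudinal models for the SF-12 and the Hip Outcome Score are not specified (SAP 9.1 and 9.2). It also protects the reading of the results. If the code is known beforehand, these steps can no longer be called blind for the implant comparison.

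**Working it through.** The documents state no figure to reproduce. The check has two parts.

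**1. Comparison of the tables**

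| SAP table | Surgical columns | Names the implant? | Deferred? |
|---|---|---|---|
| 5 | X, Y (masked) | Yes, counts of CS and SHS | No |
| 6 | CS | Yes | Yes |
| 7 | SHS | Yes | Yes |
| 10 | X, Y (masked) | In part: one re-operation line under deep infection names exchange to SHS | No |
| 12 | X, Y (masked) | No: neutral wording, "Implant exchange – IF (crossover") or (original) | No, and not needed on this account |

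Tables 6 and 7 show that the authors saw the problem, and Table 12 shows that a neutral coding was already available. Table 5 uses neither device. If it were meant only for use after unblinding, its X and Y headings would serve little purpose.

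The deferral notes also govern tables, not data. Form 5.1 feeds the screw table and form 6.1 the sliding hip screw table. An analyst who holds these forms beside the X/Y code can decode it without printing any table.

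**2. How surely the row decodes X and Y**

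Inputs:
- n = 43 per surgical arm, from the SAP Table 2 shell ("Surgical Treatment X N=43"). As a second case, n = 808/2 = 404, from the planned sample size.
- c = proportion in each arm who received the other implant. This is an assumption, since the protocol says only that it should be low; the range used is 5% to 40%.
- The cephalomedullary nail category is ignored.

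Let A ~ Binomial(n, 1 − c) be the count of CS in the arm allocated to screws, and B ~ Binomial(n, c) the count of CS in the arm allocated to sliding hip screw. The reader takes the arm with more CS to be the screw arm. This fails when A ≤ B (wrong or tied). Expected counts are n(1 − c) and nc; for example, 43 × 0.80 = 34.4 and 43 × 0.20 = 8.6.

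| c | Expected CS, screw arm vs SHS arm (n = 43) | P(A ≤ B), n = 43 | P(A ≤ B), n = 404 |
|---|---|---|---|
| 5% | 40.9 vs 2.1 | < 1e-12 | < 1e-12 |
| 10% | 38.7 vs 4.3 | < 1e-12 | < 1e-12 |
| 20% | 34.4 vs 8.6 | 5.2e-10 | < 1e-12 |
| 30% | 30.1 vs 12.9 | 8.0e-5 | < 1e-12 |
| 40% | 25.8 vs 17.2 | 0.038 | 5.7e-9 |

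A cruder rule looks at one arm only and fails when more than half of it (22 or more of 43) received the other implant. Its failure probability is 9e-18 at c = 5%, 1.3e-11 at 10% and 5.2e-6 at 20%.

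At any crossover rate that could be called low, the row identifies the arms with practical certainty. These figures measure decoding, not bias.

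**The case against.** The strongest objection is about timing. No section says when Table 5 is run. The only ordering rule is the one in SAP 8.0, and it is met if Table 5 is filled in after the blinded primary analysis. A reader might infer that the code is bound to be broken before the primary analysis, or that the Steering Committee will see the row. The documents support neither: nothing says that Table 5 comes first or that the committee receives it. This part of the objection stands. What remains is that nothing prevents the early order, while the two neighbouring tables are expressly held back.

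Second, vitamin D masking is untouched, because the row says nothing about supplement allocation. That stands, and it limits the point to one factor of the trial.

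Third, if the interaction is not significant, the surgical test is a prespecified chi-square at alpha 0.05 on adjudicated data. Knowing the code does not change that test. That also stands. A reader might add the nonunion threshold to the choices exposed, since its value is not printed. But protocol 4.8.1 and SAP Table 9 call it pre-determined, and nonunion is adjudicated by a committee that already knows the implant, so it does not belong on the list.

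**Conclusion.** The point holds in a conditional form. As written, the SAP permits Table 5 to be produced by X and Y before unblinding, and its Procedure Performed row would then reveal the implant code. That is inconsistent with the analyst blinding in protocol 4.11, with the blinded-first rule in SAP 8.0, and with the deferral of Tables 6 and 7.

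Decoding would be practically certain at low crossover. This rests on assumed rates, because the protocol gives none; at 43 per arm the reading becomes appreciably unreliable only near 40%. The consequence is confined to the implant comparison, and there to the open modelling choices and to interpretation. The size of any bias cannot be estimated from the documents. The documents do not show that blinding has been or will be lost; they show a gap that costs little to close.

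**What to change.** - Add the SAP's own note ("to be completed only after unblinding") to the Procedure Performed and Implant Manufacturer rows of Table 5.
- Keep case report form items 4.1 Q9 and Q10, and forms 5.1 and 6.1, out of the blinded analyst's extract until the blinded primary analysis is complete.
- The crossover count in Table 8 is drawn from 5.1 Q1 and 6.1 Q1. Either produce it after unblinding, or have someone outside the blinded team derive a flag (allocated implant received, yes or no) and supply only that.
- In Tables 10 and 11, replace the line that names exchange to SHS with the original/crossover wording of Table 12.

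Length of procedure and blood loss in Table 5 are weaker clues, since protocol 1.3.1 associates screws with less of both. The sponsor may consider deferring them too.

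The cost is an SAP edit, an extract rule and, if the flag is wanted early, a short task for an unblinded person. The deferred rows appear only after unblinding. Patients and sites are not affected.
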